9.0 STATISTICAL CONSIDERATIONS

9.1 General Considerations

All data listings, summaries, and analyses will be performed under the guidance and approval of the Sponsor.

Descriptive statistics will be used for all variables, as appropriate. Continuous variables will be summarized by the number of observations, mean, standard deviation (SD), median, first quartile, third quartile, minimum, and maximum. In addition to the aforementioned summary statistics, geometric mean and geometric CV will be calculated for certain PK parameters. Categorical variables will be summarized by frequency counts and percentages for each category. Unless otherwise stated, percentages will be calculated out of the total population for each treatment group and hypothesis tests will use a two-sided alpha = 0.05.

For change from baseline efficacy analyses (including the primary efficacy analysis), only participants with a baseline and at least one nonmissing postbaseline measurement will be included.

For primary analysis purposes, all efficacy endpoints will be analyzed using the Full Analysis Set (FAS). For sensitivity analysis purposes, the primary and key secondary endpoints will also be analyzed using the modified Full Analysis Set (mFAS) and Per Protocol Set, using the same statistical methodology as described in [Section 9.4.1](#) and [Section 9.4.3](#).

Additional details about the statistical methods will be provided in the SAP, which will be prepared as a separate document.

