5.1 Interim Analyses

An interim database lock (iDBL), treatment unblinding, and data analysis will be conducted after all randomized participants have either completed the Induction Treatment Period or are no longer participating in the Induction Treatment Period for one of the following reasons:

- Participant enters OLE
- Participant enters LTE
- Participant withdraws from study

This interim analysis will be referred to as the Induction Period Analysis. The following rules will be used to determine which participant records are included in the Induction Period Analysis:

- For study participants entering one of the extension periods (either LTE or OLE), the Induction Period Analysis will be limited to data on or before the later of [a] the last available date of study drug administration during the Induction Treatment Period, and [b] latest visit date as reported in EDC, up to and including Visit 7 Week 13; and in cases where Visit 8/Week 13 occurs on the same day as Visit 7 Week 13, pre-dose Visit 8 data shall also be included. For concomitant medications and adverse events the start date will determine inclusion in Induction Period Analysis (or exclusion).
- For study participants not entering an extension period, all data is included

The focus of the Induction Period Analysis will be on data associated with the Induction Treatment Period – no OLE or LTE data will be incorporated into the Induction Period Analysis other than participant disposition information related to participant flow between study periods. The Induction Period Analysis will be limited to eCRF pages associated with the Induction Treatment Period as well as external vendor data (such as central laboratory data) associated with the Induction Treatment Period.

All data for the 13-week double-blind Induction Treatment Period will be analyzed. The primary and key secondary endpoints are measured and assessed at Induction Week 13, so this analysis will be considered final for the primary and key secondary endpoints. Outputs related to the Induction Treatment Period will be clearly labeled as such. The locked data used in support of the Induction Period Analysis will be treated as final and not subject to further data alterations. The SDTM and ADaM datasets derived from the locked data and used to support Tables, Listings, and Figures will be incorporated into a final Induction Treatment Period data package.

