8. ANALYSIS SETS

The following analysis sets for the Induction Treatment Period are defined as follows:

Full Analysis Set (FAS): The FAS consists of all randomized participants receiving at least 1 dose of study treatment. Under this approach, participants are counted in the treatment group to which they were randomized, regardless of the treatment received during the study.

Modified Full Analysis Set (mFAS): For a given endpoint (see [Section 23](#), Appendix II), mFAS consists of all randomized participants who received at least 1 dose of study treatment and contribute at least one complete endpoint assessment for at least one post-baseline Induction visit. Participants will be analyzed according to the treatment to which they were randomized.

Per Protocol (PP) Set: The PP Set consists of all participants in the primary endpoint mFAS who received $\geq 80\%$ and $\leq 120\%$ of study treatment and do not have a protocol deviation preventing contribution to the primary analysis of the primary efficacy endpoint. Participants experiencing an intercurrent event during the Induction Treatment Period and not experiencing other deviations preventing contribution to the primary and key secondary analyses of the primary and key secondary efficacy endpoints will be included in the PP set and treated as non-responders in these analyses ([Section 3.5](#)).

Safety Set: The Safety Set consists of all randomized participants who received at least 1 dose of study treatment. For this population, participants are analyzed according to the treatment received, regardless of randomization. The Safety Set will be used for all safety analyses in the Induction Treatment Period.

The following analysis sets for the LTE and OLE Treatment Periods are subsets of the analysis sets of the Induction Treatment Period, as defined below:

FAS-Extension Treatment (FAS-ET) Set: The FAS-ET Set consists of all randomized participants who received at least 1 dose of study treatment in the LTE or the OLE Treatment Period. Under this approach, the original treatment groups as assigned at randomization will be used throughout LTE. In general, participants will be analyzed according to protocol-specified intended study treatment dose in FAS-ET analyses. Additional details are provided for specific analyses described elsewhere in this SAP.

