- Change from baseline in IBDQ score at Weeks 13 and 52
- Change and percentage change from baseline in lymphocyte counts at Weeks 1, 4, 8, 13, 26, 36, and 52
- Change and percentage change from baseline in Rectal Bleeding at Weeks 1, 4, 8, 10, 13, 18, 26, 36, and 52
- Change and percentage change from baseline in Stool Frequency at Weeks 1, 4, 8, 10, 13, 18, 26, 36, and 52

The first fifteen exploratory endpoints will be handled as responder analyses and analyzed similarly to the primary endpoint, per timepoint, using the CMH test with the same as-randomized stratification factors. The FAS set will be used for this purpose and treatment group comparisons (VTX002 60 mg vs placebo; VTX002 30 mg vs placebo) will be as-randomized. No adjustment for multiplicity will be made and the nominal Type 1 error rate for each hypothesis test is $\alpha=0.05$.

The last eight exploratory endpoints are quantitative. [Table 7](#) describes the analyses and analysis sets to be used for treatment group comparisons for these endpoints.

For the parameters listed in [Table 7](#), when Summary Statistics are indicated absolute values, change from baseline, and percent change from baseline will be summarized. The analysis set in the table denotes how treatment group is handled in these summaries. Additionally, figures for mean (SD) absolute value - time curve during study will be created for the following parameters:

CRP, lymphocyte counts, and neutrophil counts using normalized pooled data from both central laboratories. Separate figures will be generated for induction, LTE and OLE Treatment Periods.

Table 7. Quantitative Exploratory Endpoints and Analysis Sets

Parameter	Timepoint	Comparison	Methodology	Analysis Set
FCP (central laboratory)	Induction treatment: Weeks 1, 4, 8, 13	VTX002 60 mg vs Placebo	MMRM ^a , Summary Statistics ^b	FAS
		VTX002 30 mg vs Placebo		FAS
	LTE/OLE: Weeks 26, 36, 52 and each visit during the OLE	VTX002 60 mg vs Placebo		FAS
		VTX002 30 mg vs Placebo		FAS
CRP (central laboratory)	Induction treatment: Weeks 1, 4, 8, 13	VTX002 60 mg vs Placebo		FAS
		VTX002 30 mg vs Placebo		FAS
	LTE/OLE: Weeks 26, 36, 52 and each visit during the OLE	VTX002 60 mg vs Placebo		FAS
		VTX002 30 mg vs Placebo		FAS
PMS	Induction treatment: Weeks 4, 8, 13	VTX002 60 mg vs Placebo	FAS, PP	
		VTX002 30 mg vs Placebo	FAS-ET	
	LTE/OLE: Weeks 18, 26, 36, 52 and each visit during the OLE	VTX002 60 mg vs Placebo	FAS-ET	
		VTX002 30 mg vs Placebo	FAS-ET	

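### SAP Table 7 puts the Induction partial Mayo score comparison of 30 mg with placebo in FAS-ET, a set defined by dosing after Week 13, while 60 mg uses FAS and PP

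*SAP*

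**What the plan says.** In SAP 16.4, Table 7, the PMS block for "Induction treatment: Weeks 4, 8, 13" has two lines. The first is "VTX002 60 mg vs Placebo FAS, PP". The second is "VTX002 30 mg vs Placebo FAS-ET". The same 30 mg entry appears again in the LTE/OLE part of the PMS block, where it is unremarkable; the point here is the Induction line.

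SAP 8 defines the two sets:
- FAS: "The FAS consists of all randomized participants receiving at least 1 dose of study treatment".
- FAS-ET: it "consists of all randomized participants who received at least 1 dose of study treatment in the LTE or the OLE Treatment Period".

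SAP 4.1.3 and 4.1.4 make extension entry optional and, for both routes out of Induction, conditional on completing Week 13.

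Protocol 9.1 states that, for primary analysis purposes, "all efficacy endpoints will be analyzed using the Full Analysis Set (FAS". SAP 3.5 says exploratory endpoints will generally follow the population of the primary estimand, which is FAS. SAP 5.1 says of the Induction Period Analysis that "no OLE or LTE data will be incorporated into the Induction Period Analysis other than participant disposition information" is to be used. SAP 16.4 provides for LS means, confidence intervals and pairwise p-values for both doses by visit, and for the MMRM to use whatever data an incomplete participant has.

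**The concern.** Whether a participant belongs to FAS-ET is settled only after the last visit being analysed. Applied as written, the 30 mg Induction comparison would be made among extension entrants rather than among all randomised and dosed participants. Week 4 and Week 8 scores already recorded for early leavers would be discarded, although the MMRM is meant to use them. The placebo group would also not be the one used for 60 mg in FAS, so the two dose results could not be set side by side to judge dose response.

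**Working it through.** **1. Setting the entries side by side**

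| Table 7, Induction rows | Analysis set |
|---|---|
| FCP, 60 mg and 30 mg vs placebo | FAS, FAS |
| CRP, 60 mg and 30 mg vs placebo | FAS, FAS |
| PMS, 60 mg vs placebo | FAS, PP |
| PMS, 30 mg vs placebo | **FAS-ET** |
| IBDQ, lymphocytes, stool frequency, rectal bleeding, symptomatic response/remission | FAS |

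The PMS 30 mg cell is the only Induction entry that uses FAS-ET. SAP 18 lists two departures from the protocol (Screening day numbering and separate FCP models) and this is not one of them.

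**2. Numbers of participants**

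SAP 6 plans 63 per arm, so 30 mg plus placebo is 2 x 63 = 126 in FAS. If the planned 10% dropout all fell in Induction and every completer entered an extension, FAS-ET would hold 126 x 0.90 = 113. At an assumed non-entry of 5% to 20% it would hold 126 x 0.95 = 120 down to 126 x 0.80 = 101.

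**3. Size and direction of bias**

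The documents give no PMS variability, effect or leaving pattern, so these inputs are assumptions:
- SD of PMS change: 2 in each arm.
- True difference: -0.8 at Week 8 and -1.0 at Week 13.
- Correlation r between Week 8 and Week 13 change: 0.60, with a range of 0.50 to 0.65.
- In an arm losing a share p, a random half of the worst 2p by Week 8 change are the leavers.

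Let z be the standard normal quantile at 1 - 2p and f(z) the normal density there. The worst 2p average f(z)/(2p) SDs above the arm mean. Removing a share p with that mean lowers the Week 8 mean of those who remain by

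SD x f(z) / [2(1 - p)] = f(z)/(1 - p), with SD = 2.

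The Week 13 mean falls by r times that amount. The values needed are:
- p = 5%: 0.1755/0.95 = 0.185
- p = 8%: 0.2433/0.92 = 0.264
- p = 12%: 0.3109/0.88 = 0.353
- p = 15%: 0.3477/0.85 = 0.409

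Difference among extension entrants = true difference + r x (placebo shift - active shift):

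| Loss, placebo/active | Shift difference | Week 13, r = 0.60 | Week 13, r = 0.50 to 0.65 |
|---|---|---|---|
| 10%/10% | 0 | -1.00 | -1.00 |
| 12%/8% | 0.089 | -0.947 | -0.956 to -0.942 |
| 15%/5% | 0.224 | -0.865 | -0.888 to -0.854 |
| 8%/12% | -0.089 | -1.053 | -1.044 to -1.058 |

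Simulation under the same assumptions gives about -0.95, -0.86 and -1.05 for the three unequal cases. At Week 8 the 15%/5% case gives -0.8 + 0.224 = -0.58.

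**4. Scale**

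With SD 2 and 63 per arm, the standard error of a simple difference is 2 x sqrt(2/63) = 0.36. The Week 13 shift at 15%/5% (0.11 to 0.15) is less than half of that.

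**The case against.** The strongest reply is that this is a slip in one cell of an uneven table. Nothing in either document argues for selecting 30 mg participants on extension entry, and the general rules point to FAS. That is very likely right. A reader might infer a deliberate choice of population; the documents do not support that. But the general rules do not repair the cell either, because SAP 3.5 says only that exploratory endpoints generally follow the primary estimand, and a programmer working from Table 7 would apply the specific entry.

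It can also be said that the table layout makes the cell uncertain, since the methodology entry spans several rows and, read as text, the PMS sets can appear one column to the left. The sponsor should check the cell. Even so, there are four PMS lines with four set values, and the second falls on the Induction 30 mg line.

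The objection on size stands. The non-zero biases rest on assumed imbalances in loss, the plan's only dropout figure is an equal 10%, and the direction reverses if the active arm loses more poor performers. The offer of open-label 60 mg to Week 13 non-responders also means that poor performers who complete Week 13 may well enter FAS-ET, which the calculation ignores.

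A reader might also infer that the plan requires one three-arm model, which two different sets would make impossible. It does not: SAP 16.4 allows for more than one MMRM and the code is redacted. Whether to fit the contrasts jointly or pairwise is a preference and not part of this point.

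**Conclusion.** The Table 7 entry is wrong as written. It makes a reported by-visit comparison depend on an event after randomisation, discards observed Induction data, and departs from protocol 9.1, SAP 3.5 and the rest of the Induction rows without explanation.

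A reader might go further and conclude that the 30 mg effect will be understated. The documents do not support a direction: bias depends on which arm loses more of its poor performers, and it is nil at equal 10% loss under the assumptions above. The calculated differences of -0.86 to -1.05 against a true -1.0 illustrate what could happen and do not predict it.

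The reach is narrow. PMS change is one exploratory endpoint, tested without multiplicity control. The primary and key secondary analyses, including those for 30 mg, use FAS (SAP Table 6) and are unaffected.

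**What to change.** In SAP Table 7, change the analysis set for PMS, Induction Weeks 4, 8 and 13, 30 mg vs placebo from FAS-ET to FAS and PP, as for 60 mg, before the Induction database lock and unblinding. Leave the LTE/OLE rows unchanged. Confirm in the text of SAP 16.4 that the Induction-only MMRM uses FAS for both doses; this matters because footnote a to Table 7 also describes a second model that pools Induction and LTE visits.

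The cost is one table cell and one confirming sentence, with no effect on data collection or sample size.

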6. DETERMINATION OF SAMPLE SIZE

Approximately 189 eligible participants will be randomized in the study. The study is powered to show superiority of VTX002 60 mg to placebo with respect to clinical remission at Week 13.

Based on literature data review, the expected proportion of clinical remission at Induction Week 13 is 28% for VTX002 60 mg and 8% for placebo (Sandborn 2016; Sandborn 2020). Under these assumptions, and with a 1:1 randomization ratio, two-group chi-squared test, and two-sided significance level of 5%, a sample of 57 participants per treatment group will be sufficient to achieve at least 80% power. Adding a 10% inflation for dropouts results in 63 participants per treatment group and 189 participants in total.

All sample size calculations were conducted in SAS 9.4.

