Total MCS	LTE: Week 52	No formal comparisons, VTX002 60 mg, VTX002 30 mg, and placebo presented by visit	Summary Statistics ^b	FAS ET
IBDQ	Induction treatment: Week 13			FAS
	LTE: Week 52			FAS ET
Lymphocyte counts (central laboratory)	Induction treatment: Weeks 1, 4, 8, 13			FAS
	LTE/OLE: Weeks 26, 36, and 52			FAS ET
Stool Frequency	Induction treatment: Weeks 0, 1, 4, 8, 10, 13			FAS
	LTE/OLE: Weeks 18, 26, 36, 52 and each visit during the OLE			FAS ET

Parameter	Timepoint	Comparison	Methodology	Analysis Set
Rectal Bleeding	Induction treatment: Weeks 0, 1, 4, 8, 10, 13			FAS
	LTE/OLE: Weeks 18, 26, 36, 52 and each visit during the OLE			FAS ET
Symptomatic Response and Symptomatic Remission	Induction treatment: Week 13			FAS
	LTE/OLE: Weeks 18, 26, 36, and 52			FAS ET

^a Mixed Model for Repeated Measures, used to model change from baseline for Induction Treatment Period separately from the pooled visits across both the Induction and LTE study periods. MMRM generates statistical comparisons between treatment groups, by visit and overall.

^b Summary statistics are produced by visit for each treatment group and statistical comparisons between treatment groups are not produced.

Where mixed models with repeated measurements (MMRM) are indicated in [Table 7](#), the analysis will be applied to change from baseline in FCP (separately for Cerba and LabCorp central laboratories, Weeks 1, 4, 8, 13, 26, 36, and 52), CRP (Weeks 1, 4, 8, 13, 26, 36, and 52) and PMS (Weeks 4, 8, 13, 26, 36, and 52). The Induction Treatment Period will be handled separately from the pooled visits across both the Induction and LTE study periods. For the Induction Treatment Period, MMRM model(s) will include data from weeks 1, 4, 8 and 13. For the combined Induction and LTE study periods, MMRM model(s) will include all available data from scheduled visits across both study periods.

No imputation of missing results will be done. If a participant has any missing data whatever non-missing data is available for that participant will be used in the MMRM.

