Least square means for both change from baseline within treatment group and difference between treatment groups with respect to the outcome variable, together with standard errors, 95% CIs, and pairwise treatment group p-values (VTX002 60 mg versus placebo; VTX002 30 mg versus placebo) will be reported, by visit. Stratification factors will be added as covariates and will be handled as-randomized in all cases regardless of the analysis set being used.

Sample SAS code is presented below:

```

[REDACTED SAS CODE]
    
```

An Unstructured Covariance structure will be used in Proc Mixed. If that fails to converge, Autoregressive Covariance structure will be used. If that fails to converge, Compound Symmetry will be used. The contain method of computing degrees of freedom will be applied.

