18. DEVIATIONS FROM ANALYSIS AS DESCRIBED IN THE PROTOCOL

Study Day for Screening will run from Day -28 to Day -1, versus the Protocol SOA which says Screening will be from Day -28 to Day 0.

FCP [REDACTED] will be *separately* modelled using MMRM models due to major differences in analytical methods between these laboratories. See [Section 16.4](#).

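### Containment degrees of freedom with an unstructured covariance make the exploratory MMRM intervals slightly too narrow: negligibly for CRP and PMS, more for FCP in the smaller laboratory

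*SAP*

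**What the plan says.** SAP section 16.4 fits mixed models for repeated measures to change from baseline in FCP, CRP and PMS. It reports least-squares means, standard errors, 95% intervals and pairwise p-values against placebo at each visit.

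- Covariance: "An Unstructured Covariance structure will be used in Proc Mixed". Autoregressive and then compound symmetry follow if the model does not converge.
- Degrees of freedom: "The contain method of computing degrees of freedom will be applied".
- Covariates: "Stratification factors will be added as covariates and will be handled as-randomized in all cases".
- Induction visits: "MMRM model(s) will include data from weeks 1, 4, 8 and 13". PMS is scheduled only at Weeks 4, 8 and 13 in Table 7, so it contributes three.
- FCP is fitted "separately for Cerba and LabCorp central laboratories, Weeks 1, 4, 8, 13, 26, 36, and 52". Section 18 says this is "due to major differences in analytical methods between these laboratories".

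The sample SAS code is redacted, so it cannot be seen whether the model has a random effect. The documents do not say how many participants each laboratory served.

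**The concern.** Containment takes the degrees of freedom for a fixed effect from a random effect that contains it. The by-visit comparisons come from treatment-by-visit terms. If no random effect contains those terms, the method uses residual degrees of freedom, which is observations minus model parameters. That count grows with the number of visits per participant, although a contrast at one visit is informed mainly by the number of participants. The reference t distribution then has tails that are too light. In addition, containment leaves the standard errors uncorrected for having estimated an unstructured matrix. Both push intervals and p-values in the optimistic direction, and most so in small models. The FCP models are the ones that could be small.

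**Working it through.** **Inputs.** 189 participants: "Approximately 189 eligible participants will be randomized in the study" (SAP section 6). Three arms and three binary stratification factors. Four induction visits for FCP and CRP, three for PMS. Two-sided 5% level. The laboratory split is assumed and shown over a range, with each participant taken to belong to one laboratory.

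**The plan's own figure.** The plan gives no degrees of freedom or interval widths for these models. The only related figure is the sample size. A two-proportion calculation with 8% and 28% gives 57 per group and power 0.8019 (SAP Appendix VII: 57 and 0.802). Then 57 × 1.10 = 62.7, rounded up to 63, and 3 × 63 = 189.

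**Formulas** (V visits, N participants, complete data):

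- Residual df = N·V − (3V + 3)
- Participant-based df = N − 3 − 3 = N − 6
- Narrowing = 1 − t(0.975, residual df) / t(0.975, participant df)
- Type I error = 2·P(T > t(0.975, residual df)), with T on participant df

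For CRP: 189 × 4 − 15 = 741 against 189 − 6 = 183. The quantiles are 1.9632 and 1.9730, so the narrowing is 0.50%.

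| Model | N | V | Residual df | Participant df | Narrowing | Type I error |
|---|---|---|---|---|---|---|
| CRP | 189 | 4 | 741 | 183 | 0.50% | 5.11% |
| PMS | 189 | 3 | 555 | 183 | 0.44% | 5.10% |
| FCP, even split | 94 | 4 | 361 | 88 | 1.04% | 5.24% |
| FCP, one third | 63 | 4 | 237 | 57 | 1.62% | 5.37% |
| FCP, one quarter | 47 | 4 | 173 | 41 | 2.27% | 5.52% |
| FCP, 15% | 28 | 4 | 97 | 22 | 4.30% | 5.98% |
| FCP, 10% | 19 | 4 | 61 | 13 | 7.44% | 6.69% |

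The even split is the best case for the smaller laboratory. In any uneven split the larger laboratory lies between the CRP row and the even-split row. Removing the four participants with a baseline MMS of 4 (N = 185) moves CRP only to 0.51% and 5.12%.

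**If the redacted code has a random participant intercept.** It does not contain treatment-by-visit, so residual df still apply after removing participants: 756 − (189 + 9) = 558, against 183.

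**Simulation check.** REML fits with four visits, unstructured covariance, about 10% monotone dropout and an assumed adjacent-visit correlation of 0.7 gave these type I error rates:

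| N | Residual df | Participant df |
|---|---|---|
| 19 | 7.5% | 6.2% |
| 28 | 7.5% | 6.7% |
| 47 | 6.7% | 5.7% |
| 94 | 6.3% | 6.0% |

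The Monte Carlo standard error is about 1 to 1.5 points, so single figures are rough. The pattern is consistent with some excess remaining after the df are recounted, as unadjusted standard errors would produce.

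**The case against.** The strongest objection is that the mechanism depends on code that cannot be seen. Naming containment is compatible with a random statement, and the text's silence about random effects may be an effect of redaction. That stands as a condition on the finding. It is softened because the most likely random term, a participant intercept, would still leave about 558 degrees of freedom against 183.

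A reader might infer that the plan treats correlated visits as independent information. It does not. The unstructured matrix carries the within-participant correlation into the estimates and standard errors. Only the reference t distribution and the missing small-sample correction are at fault, which is why the effect is small.

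A reader might also infer that all the MMRM intervals are materially too narrow, or that the larger FCP figures are predictions. Where the documents supply N, the error is about half a percent. The FCP figures are scenarios. The even split gives only about 1.0%, and nothing in the documents points to a laboratory as small as 19 or 28.

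These endpoints are also exploratory. SAP section 10.4 tests them at a nominal 5% without error control, so a shift from 5.0% to 5.1–5.5% alters no controlled conclusion. That is correct and sets the grade of the point.

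The combined Induction and LTE model is left unquantified here. Only Week 13 responders enter the LTE, so complete-data figures for seven visits would not describe it.

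**Conclusion.** The point holds as a minor specification matter. If no random effect contains treatment-by-visit, the stated rule makes by-visit intervals err on the narrow side. The effect is negligible for CRP and PMS. For FCP in the smaller laboratory it is at least about 1.0% and rises as that laboratory shrinks, to 2.3% at 47 participants and 4.3% at 28. These sizes assume complete data, the 189 planned participants, the stratification factors as the only covariates and, for FCP, a laboratory split that the documents do not give. Primary and key secondary analyses use the stratified CMH test (SAP sections 16.1.3 and 16.2) and are unaffected.

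**What to change.** In SAP section 16.4, replace "The contain method of computing degrees of freedom will be applied" with a statement that Kenward-Roger degrees of freedom and standard errors are used for every MMRM fit, including fits that fall back to autoregressive or compound-symmetry covariance. This addresses both the degrees of freedom and the uncorrected standard errors; recounting the degrees of freedom alone would leave the second. Kenward-Roger was not simulated here, either under the unstructured matrix or under the fallback structures, so no claim is made that it restores exactly 5%.

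The cost is one SAP sentence and one model option, with no effect on sample size, data collection or conduct. The change should be made before the interim database lock and unblinding. Reporting the number of participants in each laboratory's FCP model would let a reader judge how much it matters.
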